IRAS	Integrated Research Application System
ISF	Investigator Site File
ISSPE	Isolated Subsegmental Pulmonary Embolism
ISTH	International Society on Thrombosis and Haemostasis
IV	Intravenous
LMWH	Low Molecular Weight Heparin
MR	Magnetic Resonance
MRC	Medical Research Council
NHS	National Health Service
NICE	National Institute for Health and Care Excellence
NIHR HTA	National Institute for Health Research Health Technology Assessment
NT-proBNP	N-terminal pro B Type Natriuretic Peptide
PACS	Picture Archiving and Communication System
PE	Pulmonary Embolism
PESI	Pulmonary Embolism Severity Index
PI	Principal Investigator
PIS	Participant Information Sheet
QALY	Quality Adjusted Life Year
RBA	Role Based Access
RCT	Randomised Controlled Trial
R&D	Research & Development
REC	Research Ethics Committee
RGT	Research Governance Team
RSI	Reference Safety Information
RUSAE	Related and Unexpected Serious Adverse Event
SAE	Serious Adverse Event

SmPC	Summary of Product Characteristics
SSPE	Subsegmental Pulmonary Embolism
ТМБ	Trial Master File
тмб	Trial Management Group
TSC	Trial Steering Committee
UoB	University of Birmingham
V/Q	Ventilation/Perfusion
VTE	Venous Thromboembolism

DEFINITIONS

Term	Description
Computed Tomography Pulmonary Angiogram (CTPA)	A medical diagnostic test that employs computed tomography to obtain an image of the pulmonary arteries.
Subsegmental Pulmonary Embolism (SSPE)	A symptomatic or incidental pulmonary embolism (single or multiple) occurring in a subsegmental pulmonary arterial branch but no larger order of vessels.
Isolated SSPE (ISSPE)	An SSPE with the absence of proximal deep vein thrombosis (DVT).
Venous thromboembolism (VTE)	A thrombus that has formed within the venous system in a limb and or the pulmonary circulation.
Major bleeding	A fatal bleeding, and/or Symptomatic bleeding in a critical area or organ, such as intracranial, intraspinal, intraocular, retroperitoneal, intra-articular or pericardial, or intramuscular with compartment syndrome, and/or Bleeding causing a fall in haemoglobin level of $20g\ L^{-1}$ (1.24 mmol L^{-1}) or more, or leading to transfusion of two or more units of whole blood or red cells.
Clinically relevant non- major bleeding (CRNMB)	Any sign or symptom of haemorrhage (e.g., more bleeding than would be expected for a clinical circumstance, including bleeding found by imaging alone) that does not fit the criteria for the ISTH definition of major bleeding but does meet at least one of the following criteria: i. requiring medical intervention by a healthcare professional ii. leading to hospitalisation or increased level of care

	iii. prompting a face to face (i.e., not just a telephone or electronic communication) evaluation ISTH major bleeding in non-surgical patients is defined as having a symptomatic presentation and: iv. Fatal bleeding, and/or v. Bleeding in a critical area or organ, such as intracranial, intraspinal, intraocular, retroperitoneal, intra-articular or pericardial, or intramuscular with compartment syndrome, and/or vi. Bleeding causing a fall in haemoglobin level of 20 g L ⁻¹ (1.24 mmol L ⁻¹) or more or leading to transfusion of two or more units of whole blood or red cells.	
Net clinical benefit	Composite of recurrent VTE and clinically relevant bleeding events.	
Active cancer	Cancer diagnosed within the past 6 months, cancer for which anticancer treatment was being given at the time of enrolment or during 6 months before randomisation, or recurrent locally advanced or metastatic cancer.	
Withholding	In relation to this trial withholding is defined as stopping the current treatment strategy of anticoagulation for at least 3 months.	

TRIAL SUMMARY

Title:

STOPping Anticoagulation for isolated or incidental subsegmental Pulmonary Embolism (STOP-APE)

Primary objective:

To determine if withholding anticoagulation is non-inferior to standard anticoagulation therapy in the treatment of isolated subsegmental pulmonary embolism (ISSPE) for preventing recurrent venous thromboembolism (VTE), or death related VTE, or superior for clinically relevant bleeding over 3 months, compared with at least 3 months of full anticoagulation.

Secondary objectives:

- Determine whether withholding anticoagulation for isolated subsegmental PE reduces harm (recurrent VTE, bleeding events) compared with at least 3 months of full anticoagulation at 6 and 12 months and impact on diagnoses of pulmonary hypertension at 12 months.
- Determine the reclassification rate of SSPE diagnoses made by acute reporting radiologists when reviewed by thoracic radiologists and formulate a set of rules to improve acute reporting radiologists' diagnoses of SSPE.
- Determine whether any radiological parameters correlate with clinical presentations or outcomes.

Economic Aims and Objectives

- Healthcare resource use: hospitalisations, bed days, unscheduled primary and secondary care visits for recurrent VTE, clinically relevant bleeding or potentially related symptoms.
- Healthcare costs.
- Health-related quality of life (EQ-5D-5L at baseline, 12 and 24 weeks).
- Cost-utility at 24 weeks (cost per QALY) and cost-effectiveness at 52 weeks (cost per VTE avoided).

Mechanistic (behavioural) Aims and Objectives

- To determine whether not treating SSPE is acceptable to patients and clinicians.
- To determine the health seeking behaviours and health utilisation of a no anticoagulation treatment strategy for isolated SSPE.

Trial Design:

An investigator led, multicentre, prospective, randomised controlled, open-label, pragmatic clinical trial designed to test both the non-inferiority and superiority objectives. A 12-month internal pilot will assess feasibility and acceptability with safety of randomisation based on acute reporting radiologists' diagnoses assessed as part of a nested computed tomography pulmonary angiogram (CTPA) study.

Participant Population and Sample Size:

1466 consenting adult patients with ISSPE diagnosed on computed tomography pulmonary angiogram (CTPA) or computed tomography (CT) thorax with intravenous (IV) contrast.

Setting:

There will be approximately 50 trial sites from secondary care clinical settings of emergency departments, ambulatory care and acute medical units within NHS hospitals in the UK.

Eligibility Criteria:

Inclusion

- Age ≥18 years
- SSPE diagnosed by the radiologist at the trial site by CTPA or CT thorax with IV contrast
- No evidence of proximal deep vein thrombosis on doppler ultrasonography or CT / MR venography
- Heart rate (<110bpm)
- Systolic blood pressure (≥100 mmHg)
- Oxygen saturation (≥90%)
- Written signed informed consent to the trial

Exclusion

- Indication for hospital admission
- >7 days empirical anticoagulation treatment immediately prior to randomisation
- <28 days since first symptoms of proven or clinically suspected COVID-19
- Known stage 5 chronic kidney disease
- Patients with active cancer defined as cancer diagnosed within the past 6 months, cancer for which anticancer treatment was being given at the time of enrolment or during 6 months before randomisation, or recurrent locally advanced or metastatic cancer
- Patients with previous unprovoked PE, thrombophilia or requiring long term anticoagulation for another reason
- Patients with a DVT / thrombus of an unusual site (e.g. upper limbs, associated with a line) that requires anticoagulation
- Patients with active bleeding
- Any condition which, in the opinion of the investigator, makes the participant unsuitable for trial entry due to prognosis/terminal illness with a projected survival of less than 3 months
- Pregnancy confirmed by positive pregnancy test or post-partum period or actively trying to conceive
- Inability to comply with the trial schedule and follow-up
- Participation in a CTIMP study

Intervention arm

Withholding anticoagulation for ISSPE for at least 3 months.

Control arm

Full dose anticoagulant treatment as standard care for at least 3 months.

Outcome Measures:

Primary Outcome

The joint (multiple) primary outcomes are a composite of; Recurrent VTE

- recurrent VTE (non-fatal)
- VTE related death (primary safety outcome)

Clinically relevant bleeding

• composite of major and clinically relevant non-major bleeding (CRNMB) (primary efficacy outcome).

Secondary Outcomes

- Recurrent VTE at 6 and 12 months.
- Clinically relevant bleeding at 6 months and 12 months (as assessed through HES records).
- Net clinical benefit composite of clinically relevant bleeding and recurrent VTE at 3 and 6 months.
- New diagnosis of pulmonary hypertension or right ventricular dysfunction within 12 months of SSPE, defined from HES clinical coding and supported where possible by additional radiological data and echocardiograms undertaken in tertiary pulmonary hypertension centres.
- All-cause mortality at 3, 6 and 12 months.
- VTE related mortality at 3, 6 and 12 months.
- Cardiovascular mortality at 3, 6 and 12 months defined as cardiac deaths (e.g., cardiogenic shock, fatal arrhythmia, cardiac rupture) and vascular deaths (e.g., VTE-related, fatal stroke, ruptured aortic aneurysm, aortic dissection).
- Reclassification rate from thoracic radiologist review.

[figure not shown]

TABLE OF CONTENTS

1.	BACKGROUND AND RATIONALE	19
1.1.	Background	19
1.2.	Trial Rationale	20
1.2.1.	Justification for participant population	20
1.2.2.	Justification for design	21
1.2.3.	Choice of intervention	21
1.2.4.	Process Evaluation	22
2.	AIMS AND OBJECTIVES	22
2.1.	Pilot Stage Objectives	22
2.2.	Main Trial Objectives	23
2.2.1.	Clinical Aims and Objectives	23
2.2.1.	1. Primary Objective	23
2.2.1.	2. Secondary Objectives	23

1. BACKGROUND AND RATIONALE

1.1.Background

Pulmonary embolism (PE) is a potentially serious condition, whereby blood clots cause a blockage of the blood supply to the lungs. PEs are often caused by blood clots in the legs and occasionally the arms (deep vein thrombosis (DVT)) breaking off and travelling to the lungs. A number of risk factors increase the chances of developing PE and/or DVT, including cancer, major surgery, pregnancy, some medications (e.g. the combined oral contraceptive pill or hormone replacement therapy), dehydration, long-distance travel and prolonged immobility. The symptoms of a PE depend on the size and location of the blood clot. A large PE can cause symptoms of breathlessness and chest pain, and the diagnosis is made using blood tests and a scan of the lungs. The treatment of PE includes anticoagulant medication ("blood thinners") that are taken over months and include: warfarin, an injectable form of heparin and direct oral anticoagulants (DOACs). These medications work by preventing new clots from forming whilst the body's own mechanisms break down the clots.

Acute pulmonary embolism (PE) is associated with significant mortality and morbidity and has a wide range of clinical severity from sudden death or haemodynamic instability through to no symptoms. The increased use and improving sensitivity of computed tomography (CT) imaging has resulted in a large increase in identification of both subsegmental PE (SSPE; embolism confined to subsegmental pulmonary vasculature) as well as incidental PE (when the CT was performed for indications other than identification of venous thromboembolism (VTE)).

To date, there have been no randomised trials to assess how subsegmental emboli should be managed, and current guidelines are based on non-randomised studies and clinical consensus. Anticoagulation of these patients may reduce short or longer term thromboembolic risk but this must be balanced against the potential increased risk of major and potentially life threatening bleeding which can occur with anticoagulant therapy.

There is growing equipoise over the value of treating small pulmonary emboli which are confined to subsegmental arteries when they are isolated, i.e. in the absence of a coexisting DVT (4). With the introduction of CT pulmonary angiography (CTPA), substantially more PEs are being diagnosed but with a fall in case fatality, suggesting over-diagnosis. Furthermore, the complication rates from anticoagulation treatment have risen by 80%, suggesting over-treatment (5). CTPA imaging diagnoses more, and smaller PEs than traditional ventilation/perfusion (V/Q) scanning.

In a trial comparing these two scanning strategies, there was no excess of recurrent VTEs during follow-up of patients whose initial V/Q scan was negative (6). A meta-analysis of uncontrolled observational studies of treating or withholding treatment in SSPE reported no clinically important difference between pooled incidences of recurrent VTE between treatment strategies (3). More recent observational data of routine care for SSPE showed very high complication rates of anticoagulation but in patients where treatment was withheld, this proved to be a safe strategy in terms of recurrent VTE (7). An international survey of clinicians using clinical vignettes found up to 30% would not treat an isolated SSPE (8). Yet there have been no clinical trials to clarify the benefits and harms of treating isolated SSPE.

Current UK guidelines for PE management from NICE (2015) (9) and from the British Thoracic Society (BTS) (10) recommend CTPA to confirm the diagnosis of PE; 9 studies in 648 patients showed sensitivity 80-100% and specificity 78-100%. This has informed the choice to use CTPA as our imaging modality to confirm subsegmental PE. However, there are concerns that over-diagnosis of SSPE may be due to incorrect interpretation of small artefacts, with some case series showing that 10% of diagnoses made by general radiologists are not supported by review from specialist respiratory radiologists (11). This trial offers the first opportunity to determine the accuracy of general radiology reporting of SSPE at sufficient scale, and clarify diagnostic criteria.

Anticoagulation is the recommended treatment in NICE guidance, initially with low molecular weight heparin (LMWH), changing to a vitamin K antagonist such as warfarin or a direct oral anticoagulant (DOAC) for 3 months thereafter (9, 12). The BTS guideline specifically considered risk stratification for outpatient management and looked at a variety of risk scores (10), concluding that the pulmonary embolism severity index (PESI) is the most well validated; no patients in low or very low risk categories had recurrent VTE at 90 days (13). This has informed our choice of PESI as a way of determining stability.

The only current guidance on the optimal treatment for patients with SSPE comes from the American College of Chest Physicians (ACCP) Antithrombotic therapy for VTE, which recommends those with a low risk of recurrent VTE and no concurrent DVT to have clinical surveillance over anticoagulation (16). However, this was based on consensus opinion rather than trial evidence.

COVID-19, the disease caused by the novel coronavirus SARS-CoV-2, has implications for a trial that tests different management strategies in SSPE. VTE is a common complication of COVID-19, in both acute and convalescent phases (31). Whist the data cited above are from patients prior to the existence of COVID-19, the issue of anticoagulating SSPE in an ambulatory convalescent phase of COVID-19 for patients who have not required hospital admission requires consideration on the same terms as other temporary causes of a prothrombotic state where there is minimal physiological impact.

Therefore, a rigorous, well-conceived and pragmatic randomised trial would be the first study to adequately address the clinical and cost-effectiveness of withholding anticoagulation in isolated SSPE compared with the usual care of full anticoagulation.

1.2. Trial Rationale

Hospital admissions for PE rose by 30% in the period 2008-2012. No individual risk factor, symptom, or clinical sign can definitively diagnose or exclude PE and therefore evaluation for PE often includes clinical decision rules, laboratory tests, and several imaging modalities. The availability of these tests, in particular the advent of CTPA, has markedly increased rates of PE diagnosis but without an increase in mortality from PE (17). In particular, with increased testing rates for PE and sensitivity of CTPA, the diagnosis of SSPE and incidental PE has increased (17). This means that understanding the utility of correctly diagnosing and treating this patient group is vital if we are to avoid over-diagnosis and excess side effects from over-treatment.

1.2.1. Justification for participant population

Patients with SSPE who are at low risk for recurrent VTE and do not require hospitalisation are those in whom there is equipoise about treatment with anticoagulation. Suitability of

out-patient management is assessed physiologically by heart rate, blood pressure and oxygen saturation. A low recurrence risk for recurrent VTE is assessed by the absence of concomitant proximal deep vein thrombosis, active malignancy (defined below), pregnancy, thrombophilia and advanced renal failure.

Cohort studies show a higher rate of larger vessel PE than SSPE among patients with actively treated cancer (19) and the overall incidence of incidental PE in this cohort may be lower than previously suspected (20). Cancer is not a single condition and certain cancers are associated with high rates of VTE recurrence (21). Given that active treatment (chemotherapy and surgery) is the major driver of VTE risks, there is no equipoise in these groups and so we will exclude patients with active treatment in progress or planned. However there is equipoise for patients who are not undergoing active treatment or have treatment planned, and therefore these patients are eligible for recruitment. In keeping with the CARAVAGGIO trial (30) we defined active cancer as cancer that had been diagnosed within the past 6 months, cancer for which anticancer treatment was being given at the time of enrolment or during 6 months before randomisation, or recurrent locally advanced or metastatic cancer.

For patients with confirmed COVID-19, data from the International Severe Acute Respiratory Infections Consortium (ISARIC) show that deterioration requiring hospital admission occurs at a mean of 14.6 days after symptom onset with a standard deviation of 8 days (32). In order to recruit patients who have most likely passed a phase of acute deterioration, we will recruit patients who are diagnosed with SSPE at least 28 days after symptom onset.

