4.2. Exclusion Criteria

- Indication for hospital admission
- <28 days since first symptoms of proven or clinically suspected COVID-19
- >7 days empirical anticoagulation treatment immediately prior to randomisation
- Known stage 5 chronic kidney disease
- Patients with active cancer defined as cancer diagnosed within the past 6 months, cancer for which anticancer treatment was being given at the time of enrolment or during 6 months before randomisation, or recurrent locally advanced or metastatic cancer
- Patients with previous unprovoked PE, thrombophilia or requiring long term anticoagulation for another reason
- Patients with a DVT / thrombus of an unusual site (e.g. upper limbs, associated with a line) that requires anticoagulation
- Patients with active bleeding
- Any condition which, in the opinion of the investigator, makes the participant unsuitable for trial entry due to prognosis/terminal illness with a projected survival of less than 3 months
- Pregnancy confirmed by positive pregnancy test or post-partum period or actively trying to conceive
- Inability to comply with the trial schedule and follow-up
- Participation in a CTIMP study

4.3.Co-enrolment

Patients cannot participate in a CTIMP study. Participation in other non-CTIMP studies is allowed.

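### Section 1.2.1 commits to excluding cancer patients with treatment planned, but the active-cancer exclusion in 4.2 does not cover planned treatment

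*Protocol*

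**What the plan says.** Section 1.2.1 names chemotherapy and surgery as the main source of VTE risk in cancer and concludes that "there is no equipoise in these groups and so we will exclude patients with active treatment in progress or planned". The next sentence states that there is "equipoise for patients who are not undergoing active treatment or have treatment planned, and therefore these patients are eligible for recruitment".

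The same paragraph then turns to the definition: "we defined active cancer as cancer that had been diagnosed within the past 6 months", followed by two further parts. The Definitions table ("Cancer diagnosed within the past 6 months, cancer for which anticancer treatment was being given at the time of enrolment"), the Trial Summary and section 4.2 ("Patients with active cancer defined as cancer diagnosed within the past 6 months") give the same three-part definition:

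1. diagnosis within the past 6 months;
2. "cancer for which anticancer treatment was being given at the time of enrolment or during 6 months before randomisation";
3. metastatic or recurrent locally advanced disease.

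Two other items in 4.2 could conceivably act as a backstop. One is "Indication for hospital admission". The other is the investigator-opinion exclusion, which applies to a participant "unsuitable for trial entry due to prognosis/terminal illness with a projected survival of less than 3 months".

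**The concern.** The rationale makes a commitment about who may be randomised, and it looks both at the present and ahead. The operative definition looks only at the past, the present and the extent of disease. Eligibility is confirmed against the listed criteria, so a site that follows 4.2 exactly can randomise a patient whom 1.2.1 places outside equipoise.

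Cancer patients who fall outside the definition are expected in this trial. Section 3.3 makes surveillance scans after cancer treatment a recruitment route, and section 6.4.1 minimises on cancer. The gap is therefore within reach of recruitment.

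At stake is the protection of a small number of participants. They could be assigned to withholding shortly before the treatment that the protocol itself identifies as driving VTE risk.

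**Working it through.** The plan gives no figure to reproduce here, so the check compares two rules and then sizes the gap under stated assumptions.

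**Step 1: the two rules.**
- Rule A (1.2.1): exclude if active treatment is in progress or planned.
- Rule B (4.2): exclude if any of three conditions holds: (1) diagnosed within 6 months; (2) treated at enrolment or in the 6 months before randomisation; (3) metastatic or recurrent locally advanced disease.

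**Step 2: combinations.** Three yes/no conditions give 2 × 2 × 2 = 8 combinations. Seven have at least one condition true and are excluded by rule B. One, with all three false, passes. A patient in that cell with treatment planned is excluded by A and eligible under B.

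**Step 3: an example (assumed dates).** Localised cancer diagnosed 14 months ago, monitored and never treated, with surgery booked for week 4 after randomisation.

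| Condition in 4.2 | Patient | Met? |
|---|---|---|
| (1) diagnosed within 6 months | 14 months | No |
| (2) treated now or in previous 6 months | never treated | No |
| (3) metastatic or recurrent locally advanced | localised | No |

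None of the three applies, so the patient passes.

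**Step 4: possible backstops.** The admission criterion concerns a need for admission at entry, not an operation weeks ahead or outpatient chemotherapy. The investigator-opinion item is tied to prognosis. No other item in 4.1 or 4.2 describes this patient.

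**Step 5: routes to anticoagulation after allocation to withholding.** Section 7.1.1 sets withholding at 3 months or more. Section 7.2 bars anticoagulants in that arm and refers to 7.3. Section 7.3 allows reassessment after central CTPA review and treatment in pregnancy; its remaining sentence concerns only the type of anticoagulant. Section 7.4 covers recurrent VTE. Starting cancer treatment triggers none of these.

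**Step 6: exposure.** With 1:1 allocation (6.4.1), the chance of withholding is about 1/2. If treatment starts at week *t*, the part of a 12-week withholding period that follows is 12 − *t* weeks: 11 for *t* = 1, 8 for *t* = 4, 4 for *t* = 8 and 0 for *t* = 12. A start at *t* = 0 is already excluded by condition (2).

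**Step 7: size.** Inputs from 13.1: 1466 patients and a 2.5-point margin. Assumed: an affected share *f* of 0.1% to 1%, and a 10-point excess VTE risk in these patients when anticoagulation is withheld.
- Patients affected: 1466 × 0.001 = 1.47, to 1466 × 0.01 = 14.66.
- Assigned to withholding: 1.47 / 2 = 0.73, to 14.66 / 2 = 7.33.
- Shift in the arm difference: *f* × 10 = 0.01 to 0.10 percentage points.
- As a share of the margin: 0.01 / 2.5 = 0.4%, to 0.10 / 2.5 = 4%.

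**The case against.** The strongest reply is that the operative rule is consistent. The same three-part definition appears in all four places, sites have one criterion to apply, and the mention of planned treatment can be read as background that the definition then puts into practice. The first part of the definition catches most patients awaiting treatment. This does not remove the conflict, because the definition still fails to deliver the exclusion of planned treatment that the rationale promises.

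The sentence that follows in 1.2.1 can also be read literally as making patients with treatment planned eligible. It is ambiguous. The more natural reading, that they are neither on treatment nor awaiting it, agrees with the sentence before it. The literal reading would contradict that sentence outright. Either way it needs rewording, and the finding does not depend on it. What stands is that the text alone cannot settle which statement the sponsor should keep.

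The third part of the definition carries no punctuation and could be read as recurrent, or locally advanced, or metastatic. That would exclude any recurrence found on surveillance and narrow the gap further, but it would not close it: the patient in the example still passes.

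Such a patient is also not locked into withholding. Section 8.5 lets a participant leave the intervention and remain in follow-up, section 8.3 records anticoagulation that is started, and section 15 preserves clinicians' duty to act. That is true, but these are provisions for withdrawal, recording and general duty. None is an eligibility rule, and none is triggered by starting cancer treatment.

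Finally, the sizes are assumed, and applying the full 10 points to every affected patient is generous given 0 to 11 weeks of exposure. That stands, and it supports the view that the statistical effect is negligible. The eligibility form is not shown either, so it may already ask about planned treatment.

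**Conclusion.** The concern holds. Section 1.2.1 and section 4.2 conflict, and the protocol is wrong as written on this point. The affected group is narrow: cancer diagnosed more than 6 months ago, no treatment for 6 months, no metastatic or recurrent locally advanced disease, and treatment scheduled but not started.

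That the gap exists follows from the text alone. Its size does not: the counts and the shift in the arm difference rest on the assumed share and the assumed excess risk, neither of which the document supplies. On those assumptions the sample size and the non-inferiority conclusion are not materially affected. The reason to correct it is that the protocol should not allow randomisation of patients for whom it states there is no equipoise. It should be corrected, but it does not threaten the trial's main result.

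**What to change.** Extend the active-cancer definition with wording such as *or for which anticancer treatment (chemotherapy or surgery) is planned*. Make the change in the Definitions table, the Trial Summary, 1.2.1 and 4.2, and add a matching item to the Registration and Randomisation Form if it has none. State a window. The 3-month withholding period in 7.1.1 is a natural choice, but the sponsor should set it. Reword the ambiguous sentence in 1.2.1 so that equipoise is claimed for patients who are not on active treatment and have none planned.

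If the sponsor does want these patients in the trial, the alternative is to delete the reference to planned treatment from 1.2.1, limit the statement about lack of equipoise to treatment in progress or recently given, and reword the ambiguous sentence to match.

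The first option costs a wording amendment in four places, one item on a form, and the loss of a few otherwise eligible patients (number not given in the document).
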